Our study, which will enroll and track a representative cohort of 2,160 persons (540 family clusters) for SARS-CoV-2 antibodies and repeatedly test them for antibodies, is significant for several reasons. First, it will allow us to track the evolution of the pandemic in the largest federally qualified health center (FQHC) in the United States. Second, we will be able to observe how the risk of infection is evolving differently in low-income underserved populations as compared to the general population. Third, repeat antibody testing of those who were seropositive in the first wave of testing will allow us to test how well antibodies maintain their presence at a second test 6-months later. There is preliminary evidence that antibodies wane over time, however current evidence is limited to few studies and small sample sizes.³ Fourth, and most importantly for scalable, generalizable, findings, we will find actionable ways to motivate repeat testing and we will be able to tailor those ways to the social and behavioral characteristics of the persons being tested.

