2.3.2 KNOWN POTENTIAL BENEFITS

All participants will receive free serology testing. Demand for testing is very high and tests are relatively expensive. In addition, accurate knowledge of serostatus is a benefit for participants. If participants increase preventative behavior in response to antibody testing then the research will also benefit others in society by reducing the spread of COVID-19.

Answering the research questions for this study is critical for designing effective and equitable COVID-19 testing programs. This study will help understand the barriers to serology testing, which will be important as serology increasingly used to inform policy. It will also help the world understand how people respond to learning their serology test results, which will help us better understand how best to use testing as a policy tool. Finally, it will provide important evidence on how antibodies wane after acute exposure, how long they remain in the system, and whether people can be re-infected. In sum, the risks of this study are small relative to the potential benefits in identifying active and recovered COVID-19 infections for public health planning.

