7.1 DISCONTINUATION OF STUDY INTERVENTION/EXPERIMENTAL MANIPULATION

Participants who decline testing initially will be offered an exit survey which will ask them for reasons for declining. We will longitudinally follow the initial cohort that completed baseline survey (including people who declined testing in wave 1) and offer an additional wave of testing 6 months after the first wave.

Participants can choose to withdraw from the study at any time, and this will be documented in their REDCap record. When a subject discontinues Wave 2 retesting but not from the study, remaining study procedures (data analysis) will be completed as indicated by the study protocol.

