9.1 STATISTICAL HYPOTHESES

The figure below provides a conceptual diagram for thinking about what factors may influence testing take-up and retesting. Testing take-up would depend on several factors, including prior beliefs about infection, health literacy, information networks, health conditions, demographics and socio-economics. We have the following hypothesis based on analysis of literature on testing for HIV and Hepatitis as well as preliminary analysis of data from our prior study:

Hypothesis 1: Those who believe that they have been infected in the past would be more likely agree to testing to confirm that they have antibodies and potential immunity; **Hypothesis 2:** People with poor health literacy will be less likely to agree to testing as they might find it daunting to understand what the test does and how to interpret results; **Hypothesis 3:** Those who are risk averse would be more likely to agree to testing as it reduces uncertainty about serostatus; **Hypothesis 4:** Those with preexisting health conditions would be more likely to agree to testing as they face higher risks from COVID-19 and thus have more to gain from learning serostatus; **Hypothesis 5:** Minorities and those in lower socio-

economic strata would be less likely to agree to testing due to fear of discrimination, lack of trust in health care/research, poor past experience, and perception of being at low risk of infection. We also generate hypotheses for facilitators to retesting (r) relative to those who take a first test **Hypothesis 1r:** Persons who practice low COVID-19 mitigation, exhibit risk-seeking and have high exposure risk may respond to a lottery retest incentive. **Hypothesis 2r:** Those persons with low income, unemployed, or have high stress or anxiety may respond most to insurance of incentives. **Hypothesis 3r:** Persons who are sero+ at baseline will be less likely to return for a retest. **Hypothesis 4r:** Lottery insurance and family messaging will induce higher retesting rates. Hypotheses 1-5 are covariates that may affect agreeing to the test. Hypotheses 1r and 2r refer to heterogeneity of treatment effects for retesting, while 3r and 4r are main effects on retesting.

Conceptual diagram

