9.2 SAMPLE SIZE DETERMINATION

We will recruit a cohort of 2,160 people (540 families), and stratify into 3 subgroups based on predictors of commitment to participation in testing programs. Randomization will be clustered by family. Sub-group membership will be based on the mean household survey response to the survey component. For the purposes of power analyses, we assume high Intra Cluster Correlation within family on uptake of repeat testing (>0.90).

Stratified Allocation Plan and Power Analysis (540 households, 2160 individuals)		
	Control	Intervention
Stratification	# households	# households
HTE Subgroup 1	60	60
HTE Subgroup 2	60	60

HTE Subgroup 3	60	60
% Seropositive in Baseline Test	10%	10%
Total Households Per Arm	180	180
Projected Average Treatment Effect Size	Reference Group	Reference+10%
Minimum Detectable Effect Size Compared to Controls (H4r)	±3%	
Detectable 3-subgroup HTE and Seropositivity (H1r, H2r, H3r)	±7%	

Assuming a similar effect size to prior studies in similar populations, we expect a 10 percentage point difference in repeat testing adherence between intervention and control groups. With 540 households, we are powered to detect as little as 3 percentage point difference between interventions and controls in the 540 households we will enroll. To assess heterogeneity of treatment effects (THE), there is more than 80% power to detect a between-subgroup difference of 7 percentage points, assuming 180 households in each sub-group.

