9.4.2 ANALYSIS OF THE SECONDARY ENDPOINT(S)

We will explore heterogeneity of treatment effects by using Model 2 to assess whether receptivity to study arm (e.g., personal messaging/loss protection) differs by significant social determinants of health identified in Hypotheses 1 through 5. To assess seroprevalence trends, we will use separate hierarchical models with a random household intercept to regress seropositivity status (yes vs. no), IgG value, and IgM value on testing time (Time 1 vs. Time 2).

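### The antibody models in Section 9.4.2 ignore that the same person is sampled twice, and no planned analysis shows persistence in Time 1 seropositives

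*Combined protocol and SAP*

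**What the plan says.** Section 9.4.2 assesses seroprevalence trends with "separate hierarchical models with a random household intercept to regress seropositivity status (yes vs. no), IgG value, and IgM value on testing time" (Time 1 v Time 2). It states no person-level term, paired analysis or robust variance. The household-clustered bootstrap in Section 9.4.1 is specified for attendance Models 4a and 4b only. Model 3 uses Time 1 serostatus only to predict attendance, and Section 9.4.8 plans no exploratory analyses.

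The design is nevertheless a repeat measure. Section 8.1 gives each tested person a unique Study ID and recalls participants six months after the first test. Two passages suggest that the people sampled will differ between waves. Hypothesis 3r in Section 9.1 reads "Persons who are sero+ at baseline will be less likely to return for a retest", and Section 7.1 offers the second wave to the whole survey cohort, "including people who declined testing in wave 1".

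On persistence, Section 2.1 says that "repeat antibody testing of those who were seropositive in the first wave of testing" will test how well antibodies last, and Section 2.3.2 says "it will provide important evidence on how antibodies wane after acute exposure". The endpoint table in Section 3 lists seropositive status, but neither persistence nor waning.

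**The concern.** A household intercept treats a person's two samples as no more alike than samples from two relatives. Three things follow.

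- The standard error of the time contrast does not reflect the pairing. It is usually too wide, so a real small change could be missed.
- The time coefficient combines change within people with a change in who was sampled. Seroprevalence could appear to fall although nobody's status changed.
- Loss of antibodies in positives is netted against conversion in negatives, so the coefficient does not answer the question that Section 2.1 raises.

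**Working it through.** The plan gives no precision or power figure for the antibody analysis, so there is none to reproduce. Section 9.2 supplies 2,160 people in 540 families (4 per family), 10% "Seropositive in Baseline Test", and "we assume high Intra Cluster Correlation within family on uptake of repeat testing (>0.90". Variance shares, return rates and reversion rates are assumptions.

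**1. Standard error, continuous value, everyone returns, relatives change independently.** Let p be the person variance and e the residual variance. Of the 7 within-household degrees of freedom (4 people x 2 times), 3 are between people with mean square e + 2p, and 4 are within people with mean square e. A household-only fit pools them: (3(e + 2p) + 4e)/7 = e + (6/7)p. The true error of the time contrast involves e alone. The ratio of reported to true standard error is therefore sqrt(1 + (6/7)p/e).

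| Household / person / residual share | Ratio |
|---|---|
| 0.2 / 0.3 / 0.5 | sqrt(1 + 0.514) = 1.23 |
| 0.2 / 0.5 / 0.3 | sqrt(1 + 1.429) = 1.56 |
| 0.2 / 0.6 / 0.2 | sqrt(1 + 2.571) = 1.89 |

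Simulation agrees: at 0.2/0.6/0.2 the household-only standard error was 0.0257 and that of the model with a person effect 0.0136, a ratio of 1.89. For seropositivity, a simulated household-intercept logistic model gave a standard error 1.67 times the empirical one at about 76% persistence, and 2.82 times at about 92%.

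**2. The same, when households change together.** Add a household-by-time variance h. The true error then involves e + 4h, the household-only model reports e + (6/7)p + (4/7)h, and a model with person and household intercepts reports e + h.

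| Household / person / residual / h | Household-only ratio | Person + household ratio |
|---|---|---|
| 0.2 / 0.45 / 0.3 / 0.05 | sqrt(0.714/0.500) = 1.20 | sqrt(0.35/0.50) = 0.84 |
| 0.2 / 0.4 / 0.3 / 0.10 | sqrt(0.700/0.700) = 1.00 | sqrt(0.40/0.70) = 0.76 |

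In the second row the planned standard error is right. A person intercept with model-based errors would be too narrow in both rows, with type I error of about 10% and 14%.

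**3. Who returns, with nobody changing status.** If 60% of negatives and a share a of positives return, raw Time 2 prevalence is 0.1a/(0.1a + 0.9 x 0.6). That is 8.5% for a = 0.5 and 6.9% for a = 0.4, against 10%. The planned logistic model was fitted to simulated data (540 households of 4, household correlation of serostatus 0.1 to 0.5, 300 datasets per cell):

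| Return, positives v negatives | Relatives return separately | Household returns all-or-none |
|---|---|---|
| 40% v 60% | OR 0.63-0.64, significant in 74%-95% | OR 0.90-0.92, never significant |
| 50% v 60% | OR 0.81-0.82, significant in 8%-17% | OR 0.94-0.96, never significant |

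In the all-or-none column, a household's return probability falls from 60% with no positive member to 40% or 50% with all positive. A second simulation with 50% v 70% return rejected the null in 30%-59% of trials when relatives returned separately. When households returned together (50% with any positive member, 70% with none) it rejected in 1%-4%. For IgG with separate return at 50% v 70%, a person effect cut the spurious fall from 0.018-0.032 SD to within 0.003 SD.

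**4. Netting.** At 10% prevalence, reversion r in positives is cancelled when 0.1r = 0.9c, so c = r/9. For r = 10%, 30% and 50%, c = 1.1%, 3.3% and 5.6%. In people, 30% of 216 positives is about 65, and so is 3.3% of 1,944 negatives.

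**The case against.** The models are labelled as a seroprevalence trend. For that target a population contrast is legitimate, and first-time testers at the second wave are not in themselves a fault. Persistence is rationale and benefit text, not a listed endpoint. Both statements stand. They make the gap a missing analysis, not a failed endpoint.

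A reader might infer that the planned standard error is certainly too wide. The documents do not support that. They say nothing about whether relatives change together, and infection can plausibly cluster in families. With an assumed household-by-time share of 0.10 the planned standard error is correct. By the same reasoning, adding a person intercept and trusting its model-based error could turn a conservative test into an anti-conservative one.

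A reader might also infer that selective return will probably produce a false fall in seroprevalence. The large odds ratios above need relatives to return separately and a 20-point gap in return. Neither figure is in the plan, and the one figure that is, the family correlation above 0.90, points the other way.

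None of this answers the netting: whatever the standard error and whoever returns, one coefficient cannot separate reversion from conversion.

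**Conclusion.** The concern holds as a minor point on the secondary antibody analysis.

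- **Pairing:** ignored. The reported standard error is about 1.23 to 1.89 times the true one under full return, independent change and the assumed shares. The excess falls to nil as change clusters by household.
- **Who was tested:** mixed with change. The effect is material if relatives return separately and small if households return together.
- **Persistence:** the pooled contrast cannot show it, and no other planned analysis does.

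Hypotheses 1r to 4r concern attendance, and this point makes no claim about them. Models 4a and 4b also carry only a household intercept over two times, but their probability differences have household-clustered bootstrap intervals.

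**What to change.** Keep the Time 1 v Time 2 contrast as the trend summary, and add to Section 9.4.2:

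1. A person-level intercept nested in household, or a paired difference among people tested twice. The paired difference is the safer choice for seropositivity, where most pairs will agree and the logistic model may not converge.
2. Intervals for all three outcomes from a household-clustered bootstrap (already planned for Models 4a and 4b) or a household-robust variance, not from the model-based standard error alone.
3. Among people tested twice and positive at Time 1: the share still seropositive, and the change in log IgG and log IgM.
4. Among people tested twice and negative at Time 1: the share converting, without attributing it to infection alone.
5. Time 1 results for returners and non-returners side by side.

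The cost is SAP wording and a little more analysis. No new data are needed, because the Study ID links a person's samples. The persistence subset is small: 216 x 0.4 = 86, x 0.5 = 108 or x 0.8 = 173 people at assumed return rates. With 30% reversion, 1.96 x sqrt(0.3 x 0.7/n) gives half-widths of 9.7, 8.6 and 6.8 points before household clustering. Items 3 and 4 describe returners only. A person effect handles return that depends on observed Time 1 values, but not return that depends on unseen Time 2 status.

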9.4.3 SAFETY ANALYSES

The Principal Investigator (PI) will be responsible for ensuring participants' safety on a daily basis. We will establish a Data Safety and Monitoring Board (DSMB) in the first month of the project. The Data and Safety Monitoring Board (DSMB) will act in an advisory capacity to the NIA Director to monitor

participant safety, evaluate the progress of the study, to review procedures for maintaining the confidentiality of data, the quality of data collection, management, and analyses. We will establish a Data Safety and Monitoring Board (DSMB) in the first month of the project. The board will be composed of experts in behavioral economics, a physician with expertise in COVID-19, and a biostatistician. The DSMB is granted full power to recommend discontinuation of the study to the consolidated IRB, if safety concerns are found. A detailed Data and Safety Monitoring Plan will be submitted for IRB approval prior to the accrual of human subjects.

9.4.4 BASELINE DESCRIPTIVE STATISTICS

Intervention groups will be compared on baseline characteristics (e.g., demographics, laboratory measurements, behavioral characteristics) using descriptive statistics.

9.4.5 PLANNED INTERIM ANALYSES

There will be no interim analysis on the primary outcome. However, we will look at demographic characteristics of participants after 1 week of testing to determine stratification thresholds.

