4.1 OVERALL DESIGN

Social determinants need to be understood in the context of actionable facilitators (things COVID-19 policymakers can do) to encourage repeat testing. We will study two types of facilitators (messaging and financial incentives) and evaluate the heterogeneity of treatment response based on the characteristics of those tested. We will conduct a 2 x 2 (messaging x financial incentive) factorial design (Aim 3) that stratifies on social and behavioral determinants (Aim 2) collected as part of an initial survey (Aim 1). We have been studying ways to identify powerful incentives for repeated health behaviors. We have found that providing at-risk incentives that can be insured with repeat health behavior outperforms direct cash payments of the same expected value. Individuals were 70% more likely to return to a health screening when insuring against losing a baseline incentive than they were when paid cash ($p < 0.01$).⁴ In addition, in a recent study we showed that disadvantaged patients at a federally-qualified health center were more likely to repeat a health behavior twice each week over 12 weeks when repetition

was insuring against losing a weekly incentive than if they were paid equivalently in cash (see Figure 1; $p < 0.05$).

5

Figure 1. Insurance (loss protection) vs. cash (control) incentive for repeat health behavior among disadvantaged persons (N = 151)

2 x 2 Stratified Randomization

Messaging (Factor 1): We will develop simple messaging that frames the decision to test in terms of either: (i) family risk, or, (ii) personal risk. These methods will be piloted, but will be of the form "Antibody testing will help you understand your family's risk of getting COVID-19"; and, "Antibody testing will help you understand your risk of getting COVID-19". Family risk framing may engender concern for loved ones. It may also make it easier to mentally simulate family burdens with COVID-19 such as knowing how several people in the family becoming sick could adversely affect the lives of everyone in the family. We hypothesize that the family framing will result in greater uptake of testing and greater repeat testing.

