6.1.2 ADMINISTRATION AND/OR DOSING

Clinical research coordinators will be blinded to the participant's condition. Participants will receive information on the intervention arm as part of the initial recruitment phone call and will also receive a reminder at the time of initial test visit. This will be provided as either a sealed envelope or email/text (based on participant preference) with test return instructions and information on the incentive they will be receiving. Lotteries will be played and incentives paid at the time of Wave 2 retesting.

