6.3 MEASURES TO MINIMIZE BIAS: RANDOMIZATION AND BLINDING

Randomization will occur at the beginning of the study using the following steps:

NIH Protocol Template for Behavioral and Social Sciences Research Involving Humans

- We will receive a list of 6,222 names from AltaMed Health Services (3074 in the “far” group and 3148 in the “near” group; “far”/“near” based on further/nearer than the median distance of LA AltaMed patient zip codes from the testing site’s zip code).
 - Using this list, The Henne Group will reach out to these participants asking if they would like to participate in the study and have a child in the household.
 - Each household will be assigned a study ID; each participant will have a Study ID number as well as a medical record number (for patients only) from AltaMed to incorporate into the EHR.
 - A list of eligible participants will be available in our HIPAA compliant version of REDCap with their name, research ID and script option (4 options- 2 for messaging/ 2 for financial incentives)
 - Using the randomization feature in REDCap, we will be able to randomize the scripts that each participant will receive.
- Onsite Clinical research coordinators will be blinded to the participant’s condition.

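### Stratification thresholds are set a week into testing, after the early families have been randomised; the strata are defined in two ways, and Models 4a/4b leave them out

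*Combined protocol and SAP*

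**What the plan says.** **Design claim.** Section 4.1 has a subheading announcing a stratified 2 x 2 randomisation and describes a factorial design "that stratifies on social and behavioral determinants (Aim 2) collected as part of an initial survey (Aim 1"). Section 9.2 will "stratify into 3 subgroups based on predictors of commitment to participation in testing programs" and adds: "Sub-group membership will be based on the mean household survey response to the survey component". Its table is titled as a stratified allocation plan, with 60 households in each of three HTE subgroups per arm.

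**Randomisation.** Section 6.3 states: "Randomization will occur at the beginning of the study using the following steps". The last allocation step is: "Using the randomization feature in REDCap, we will be able to randomize the scripts that each participant will receive". No stratum appears in the steps. The only grouping there is near/far, which belongs to the sampling list.

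**Disclosure.** Section 6.1.2: "Participants will receive information on the intervention arm as part of the initial recruitment phone call".

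**Thresholds.** Section 9.4.5 rules out an interim analysis of the primary outcome and then says "we will look at demographic characteristics of participants after 1 week of testing to determine stratification thresholds".

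**Analysis.** In section 9.4.1, Model 4a has testing time, incentive, messaging, the two interactions with time, and a household random intercept. Model 4b has testing time, three arm terms, three arm-by-time terms and the same intercept. The bootstrap is clustered by household, with no mention of strata.

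**The concern.** A stratum can shape allocation only if it exists when the arm is assigned. Here the arm is given out on the recruitment call and the thresholds come after a week of testing, so the order is reversed for every family handled by then.

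The plan also has two definitions of the stratum. Section 9.2 uses a survey score meant to predict commitment to testing; section 9.4.5 uses participants' demographics. A programmer could not build the REDCap strata from this text.

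The three-level stratum also appears in no specified model. Model 2 and the heterogeneity analysis use individual survey items. If allocation is stratified on something that predicts attendance and the analysis ignores it, reported standard errors for arm differences come out too large.

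**Working it through.** **1. Order of events**

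| Step | Source | When |
|---|---|---|
| Baseline survey completed | 5.5 | recruitment call, before testing is offered |
| Scripts randomised | 6.3 | beginning of the study |
| Arm disclosed | 6.1.2 | recruitment call |
| First tests | 8.1 | later appointment |
| Thresholds set | 9.4.5 | after 1 week of testing |

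Every family tested in week 1, and every family called but not yet tested, has an arm before the thresholds exist.

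**2. How many families.** The plan gives no accrual rate for the trial. As an assumption, take the pilot pace in 4.1: just over 50 families in 2 days, or 25 a day.
- 5 testing days: 125/540 = 23%.
- 7 testing days: 175/540 = 32%.

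This leaves out families called but not yet tested. If 6.3 means that all households are randomised up front, the share is 100%.

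**3. Precision for an arm difference at one time.** The plan gives no figure for the gain from stratification, so there is nothing to reproduce. Inputs from 9.2: 540 households, 2,160/540 = 4 people each, ICC 0.90 (the plan says above 0.90), a 10-point effect. Assumptions: 270 v 270 households for one factor, mean retest rate 50%, two-sided alpha 0.05, three equal strata.

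- Variance of a household mean: 0.25 × (1 + 3 × 0.90)/4 = 0.23125.
- Unadjusted SE: √(2 × 0.23125/270) = 0.0414. Power = Φ(0.10/0.0414 − 1.96) = 67.6%.
- Share explained by strata: R² = between-stratum variance/0.23125. The SE ratio is √(1 − R²).
- Example, 30/50/70%: (0.04 + 0 + 0.04)/3 = 0.0267; R² = 0.115; ratio 0.941.

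| Assumed retest rates | R² | Reported SE falls by | Power, 10 points | Households (540 × R²) |
|---|---|---|---|---|
| 45/50/55% | 0.007 | 0.4% | 67.9% | 4 |
| 40/50/60% | 0.029 | 1.5% | 68.9% | 16 |
| 30/50/70% | 0.115 | 6% | 72.9% | 62 |
| 20/50/80% | 0.259 | 14% | 80.2% | 140 |

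The last column is how many fewer households an adjusted analysis would need for the same reported precision.

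**4. Only part of the sample stratified.** This was simulated on household means (a linear proxy for the mixed logistic models), with 540 households, 3,000 runs per scenario, and 25% allocated without strata.

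| Rates | True SD, without v with stratum | Reported SE, without v with | Power, without v with | Type I error without |
|---|---|---|---|---|
| 40/50/60% | 0.0406 v 0.0406 | 0.0412 v 0.0406 | 67.9 v 69.1% | 3.8% |
| 30/50/70% | 0.0396 v 0.0389 | 0.0414 v 0.0389 | 68.9 v 73.2% | 3.8% |
| 20/50/80% | 0.0385 v 0.0367 | 0.0416 v 0.0358 | 67.2 v 78.7% | 3.0% |

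The estimate itself improves little. What the omission mostly does is overstate the SE. With no family stratified, the unadjusted type I error was 4.4 to 5.5%, close to nominal.

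**5. Interaction terms.** Write a household's mean as stratum effect + household effect + time and arm terms. The time-by-arm interaction compares changes from Time 1 to Time 2. The stratum effect is the same at both times, so it cancels, and a stratum main effect adds nothing. A mixed logistic simulation of Model 4a agrees (540 households of 4, random-intercept SD 2 on the logit scale, both times observed for all, 120 runs per scenario). The SD of the time-by-incentive estimate without v with the stratum was 0.148 v 0.148 (40/50/60%), 0.154 v 0.154 (30/50/70%) and 0.188 v 0.189 (20/50/80%).

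**The case against.** A reader might infer that the stratified design is not delivered at all, that its precision is lost, or that the comparison is biased. The documents do not support any of these.

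- **Not delivered.** This is certain only for families randomised before the thresholds exist. Later families could still be stratified, and the text does not say whether they are.
- **Purpose of the thresholds.** Section 9.4.5 does not say they govern allocation. The table in 9.2 labels the strata as HTE subgroups, so they may be analysis cut-points, in which case their timing does no harm to allocation. That reading is possible, but it conflicts with the subheading in 4.1 and the table title in 9.2, so the text needs reconciling either way.
- **Precision lost.** The compared coefficients, β4 and β5 in Model 4a and β5 to β7 in 4b, are interactions with time, where the household intercept already absorbs the stratum. This objection stands. The gain is confined to arm differences at one time: uptake at Time 1, retest probability at Time 2, and the bootstrapped probability differences if that is what they are.
- **Bias.** The unadjusted analysis is valid; it errs, if at all, towards conservatism.
- **Near/far omitted.** Distance is a sampling stratum and is not declared as a randomisation stratum. Leaving it out is no inconsistency.
- **Feasibility.** The documents describe no pilot survey scores from which to take tertiles, and scoring must happen on the call before the arm is given. Both are real constraints on the fix.

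**Conclusion.** The point holds as a conflict in timing and definition. As written, families randomised before the thresholds exist cannot be stratified as 4.1 and 9.2 claim. At the pilot pace that is about 23 to 32% of families, and all of them if randomisation is done up front. Section 6.3 supplies no strata, and 9.2 and 9.4.5 disagree on what the strata are.

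Leaving the stratum out of Models 4a and 4b is a lesser matter. For arm differences at one time, including it would reduce the reported SE by 0.4 to 1.5% with weak strata, 6% at 30/50/70% and 14% at 20/50/80%. These rest on assumed stratum rates, a 50% mean rate, ICC 0.90 and a linear approximation. There is no gain for the time-by-arm interactions and no threat to validity. The change is worth making because it is cheap and settles what was randomised.

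**What to change.** 1. Define the three strata by pre-specified cut-points on the baseline survey score, fixed before the first randomisation. Section 5.5 has one adult per household answer the survey, so 9.2 should say what the household mean is taken over.
2. Name these strata in 6.3 and load them in a REDCap randomisation with the household as unit. The survey is completed before testing is offered, so the score can exist before the arm is assigned.
3. Delete the week-1 threshold step from 9.4.5.
4. Add the stratum as a fixed effect in Models 4a and 4b, and resample households within stratum in the bootstrap. State which probability differences are reported. A near/far term is optional.
5. If the 9.4.5 thresholds are meant only for the HTE analysis, say so there and remove the stratified-allocation claim from 4.1 and 9.2, and wherever the design wording is repeated (4.3, 6.1.1).

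**Cost.** Mostly wording, plus one operational change: the caller's system must score the survey before assigning the arm. Cut-points set in advance may give unequal strata, so the equal 60-household cells in 9.2 may not be met.
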